7.4.1.2 Atezolizumab – combination drug

A fixed dose of 1200 mg atezolizumab will be administered through intravenous (i.v.) infusion on Day 1 of each 21-day cycle until disease progression, unacceptable toxicity or consent withdrawal.

23 MAY 2023 Version 6.0 Page: 55 of 181

Administration of atezolizumab will be performed in a setting with emergency medical facilities and staff who are trained to monitor for and respond to medical emergencies. For more detailed information regarding administration, refer to the investigator's brochure.

The initial dose of atezolizumab will be delivered over $60 (\pm 15)$ minutes. If the first infusion in Cycle 1 is tolerated without infusion-associated adverse events, the second infusion in Cycle 2 may be delivered over $30 (\pm 10)$ minutes. If the 30-minute infusion is well tolerated, all infusions in the subsequent cycles may be delivered over $30 (\pm 10)$ minutes. For the first infusion, the patient's vital signs (heart rate, respiratory rate and blood pressure) should be monitored 60 minutes before, during (every $15 [\pm 5]$ minutes), and $30 (\pm 10)$ minutes after the infusion. For subsequent infusions, vital signs will be collected within 60 minutes before infusion and at the end of the infusion. Patients will be informed about the possibility of delayed post-infusion symptoms and instructed to contact their study physician if they develop such symptoms.

No pre-medication will be allowed for the first dose of atezolizumab. Pre-medication may be administered for Cycles ≥ 2 at the discretion of the treating physician in case of previous infusion reaction. Pre-medication should be recorded in eCRF as concomitant medication.

For the management of infusion-related reactions see the specific section in Section 7.4.3.3.

Most common adverse reactions (\geq 20%) in patients with locally advanced or metastatic urothelial carcinoma were: fatigue, decreased appetite, nausea, urinary tract infection, constipation, diarrhea and pyrexia. Atezolizumab has been associated with risks such as the following: infusion-related reactions and immune-related hepatitis, pneumonitis, colitis, pancreatitis, diabetes mellitus, hypothyroidism, hyperthyroidism, adrenal insufficiency, Guillain-Barré syndrome, myasthenic syndrome or myasthenia gravis, myocarditis and meningoencephalitis. Immune-related adverse reactions (pneumonitis, hepatitis, colitis, endocrinopathies, other immune-related adverse reactions) requiring systemic corticosteroids or hormone replacement therapy occurred in < 20% patients. In addition, systemic immune activation (described below) is a potential risk associated with atezolizumab when given in combination with other immunomodulating agents.

Any overdose or incorrect administration of combination drug should be noted on the Study Drug Administration electronic Case Report Form (eCRF). Adverse events associated with an overdose or incorrect administration of study drug should be recorded on the Adverse Event eCRF.

Guidelines for dose modification, treatment interruption or discontinuation and for the management of specific adverse events are provided in a specific section in Section 7.4.3.3.

7.4.2 Justification of selected doses

Rogaratinib: rogaratinib dose of 800 mg b.i.d. was chosen for further clinical development based on pharmacokinetic, biomarker, safety and anti-tumor activity in the Phase 1 dose escalation study 16443.

Atezolizumab: the approved dose of atezolizumab will be used in this study.

23 MAY 2023 Version 6.0 Page: 56 of 181

7.4.3 Dose modifications

7.4.3.1 Dose limiting toxicities (DLTs)

A DLT is defined as any of the following TEAEs occurring during Cycle 1 and regarded by the investigators and/or sponsor to be related to rogaratinib or atezolizumab. The CTCAE v 4.03 will be used to assess toxicities / adverse events.

Hematological

- Absolute neutrophil count (ANC) < 500/mm³ for more than 7 days
- Febrile neutropenia (a disorder characterized by an ANC $< 1,000/\text{mm}^3$ and single temperature ≥ 38.3 °C or sustained temperature of ≥ 38.0 °C for more than 1 hour)
- Platelets $< 25,000/\text{mm}^3$
- Hemoglobin < 8.0 g/dL
- Grade 3 hemorrhage associated with thrombocytopenia of \geq Grade 3

Non-hematological

- Any non-hematologic Grade 3 or higher toxicity except:
 - o Grade 3 nausea, vomiting, and fatigue that resolve within 72 hours with or without supportive care.
 - o Grade 3 diarrhea will be classified as DLTs if not resolved to Grade ≤ 2 or baseline following dose interruption of rogaratinib and/or withholding atezolizumab within 3 days with or without supportive care.
 - Laboratory abnormalities of any grade will not be considered toxicity unless deemed clinically significant by the investigator.
 - o Grade 3 hypothyroidism
- Any grade myasthenic syndrome/myasthenia gravis, Guillain-Barré or meningoencephalitis.
- Decrease of three lines or more in visual acuity scales, Grade 2 or higher ocular pain or discomfort, or symptomatic retinal disorders including retinal detachment, RPED, central serous retinopathy or retinal vein occlusions.
- Grade 2 with AST or ALT >3 x ULN and up to 5 x ULN or total bilirubin greater than 1.5 and up to 3 x ULN in absence of an alternative explanations for these elevations.
- Any toxicity not resolving within 21 days at ≤Grade 1 with or without supportive care.

23 MAY 2023 Version 6.0 Page: 57 of 181

Miscellaneous

- In case an unexpected drug-related toxicity is seen more frequently, this toxicity may be declared a DLT for the remainder of the study after thorough consultation between the investigator and the sponsor.
- Any rogaratinib-related toxicity that, at the discretion of the investigator, or his designated associate(s), is thought to warrant withholding the drug for more than 3 consecutive days.
- Such toxicities might be Grade 1 or Grade 2 toxicities which interfere with the activities of daily life (e.g. long-lasting fatigue, or anorexia), making a dose reduction necessary in order to ensure the patient's compliance.
- Inability to start Cycle 2 Day 1 due to clinically relevant toxicity.

For certain toxicities such as laboratory assessments without a clear clinical correlation (e.g. lipase increase without signs of a clinical pancreatitis) or in patients that violated the protocol, a discussion between the investigator and the sponsor may take place if that adverse event should be regarded as DLT necessitating dose reduction.

7.4.3.2 Dose modifications of rogaratinib

Dose of rogaratinib may be interrupted / delayed or reduced in case of clinically significant toxicities that are related to study drug therapy. The intensity of toxicities will be graded using the CTCAE v 4.03.

If a patient experiences a DLT during Cycle 1 (Days 1-21), the next dose of rogaratinib can be delayed for up to 21 days. This is permitted also in case of Grade 3 toxicities that are not defined as withdrawal criteria and that are persisting ≤ 7 days.

All patients who are re-treated following a DLT should undergo dose reduction of rogaratinib (see Table 7–2).

If the toxicity resolves within 21 days after the planned treatment date to \leq Grade 1 re-starting rogaratinib at 1 dose level below the current dose can be considered (see Table 7–2). If such an improvement is not observed, the study treatment should be permanently discontinued.

Patients who experience a Grade 4 non-hematological toxicity, and any other toxicity defined as withdrawal criteria will be permanently withdrawn from the study treatment.

If a patient experiences clinically relevant toxicity after Cycle 1, the next dose of rogaratinib can be delayed for up to 21 days. This is permitted also in case of Grade 3 toxicities that are not defined as withdrawal criteria and that are persisting ≤ 7 days. If the toxicity resolves within 21 days after the planned treatment date to \leq Grade 1 or baseline, reduction of the next dosing of rogaratinib by 1 dose level below the current dose (see Table 7–2) can be considered.

Patients requiring dose reduction to less than 400 mg b.i.d. should be permanently withdrawn from the study treatment.

23 MAY 2023 Version 6.0 Page: 58 of 181

Table 7–2: Dose levels of rogaratinib (BAY 1163877)

Level	Dose
Starting level	800 mg b.i.d.
-1	600 mg b.i.d.
-2	400 mg b.i.d.

b.i.d = Twice daily, bis in die.

Dose modifications will be based on the highest intensity grade of AE since last contact.

If a patient experiences multiple toxicities, dose modification should be according to the toxicity with the highest grade.

- In case of multiple toxicities of the same grade, investigator should modify the dose using the most conservative approach, i.e. the lowest recommended dose.
- Patients in whom doses are interrupted due to toxicities should be followed up within 7 to 10 days to re-assess toxicities, if not specified otherwise.
- Patients requiring dose reduction of rogaratinib, with the exception of dose reduction due to liver toxicities, may have the dose re-escalated by one dose level if they have been on a stable dose for 3 weeks or more without further toxicities requiring dose modification and if toxicity has resolved to baseline.
- Patients requiring a dose interruption of rogaratinib due to toxicity > 21 days from the next intended dose or due to other reasons for > 31 days from the next intended dose will be withdrawn from the study treatment.
- If further dose reductions below level -2 are needed, patients will be withdrawn from the study treatment.
- If a dose of rogaratinib is missed, the prescribed dose should be taken as soon as the patient remembers and up to 3 hours after the usual time. If this is not possible, missed doses should not be replaced and the patient should continue with the next dose as planned.

The cycle duration will consist of 21 days of treatment with rogaratinib (interruptions will not prolong the duration of a cycle).

Detailed dose adjustments for toxicities are described in Table 7–3. Patients who experience a Grade 4 toxicity must discontinue study drug permanently.

23 MAY 2023 Version 6.0 Page: 59 of 181

Table 7–3: Guidance for dose modification of rogaratinib due to toxicity (excluding hyperphosphatemia, liver toxicity, retinal disorders)

Grade ^a	Dose delay	Dose modification
1 – 2 ^b	Treat as scheduled	No change
3	Delay c until recovery to \leq Grade 1	Decrease by 1 dose level ^d
4	Discontinue study treatment permanently	Discontinue study treatment permanently

a: Excludes alopecia, fatigue, nausea/vomiting if adequately controlled by antiemetic treatments. Laboratory abnormalities of any grade will not be considered toxicity unless deemed clinically significant by the investigator. In addition, specific dose modification rules for hyperphosphatemia, liver toxicity and retinal disorders are given in the following sections.

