- O Any decrease in visual acuity, ocular pain or discomfort, or symptomatic retinal disorders including retinal detachment / retinal pigment epithelial detachment / central serous retinopathy / retinal vein occlusion classified analog to CTCAE v.4.03 as Grade 2 or higher. Based on the individual benefit risk assessment and after discussion with the sponsor, patient may interrupt treatment until recovery to at least Grade 1 and then treatment may be resumed at one dose level below. Patients with low visual acuity at baseline (best corrected visual acuity worse than 20/40 and up to 20/200) have to undergo individual clinical evaluation to determine the maintenance in the study, according to investigator's judgement and based on the individual benefit risk

23 MAY 2023 Version 6.0 Page: 49 of 181

assessment.

- o Liver toxicity with AST or ALT > 3 x ULN with concomitant bilirubin > 2 x ULN in the absence of an alternative explanation for these elevations.
- \circ \geq Grade 3 liver toxicity with ALT or AST > 5 x ULN and/or total bilirubin > 3 x ULN in the absence of an alternative explanation for these elevations.
- Any grade myasthenic syndrome/myasthenia gravis, Guillain-Barré or meningoencephalitis.
- o Any grade of recurrent symptomatic pancreatitis.
- o Newly diagnosed soft tissue mineralization suspected to be caused by rogaratinib.
- o Grade 4 non-hematological toxicity (laboratory abnormalities of any grade will not be considered toxicity unless deemed clinically significant by the investigator).
- o Grade 3 or higher non hematologic toxicity atezolizumab-related and requiring treatment discontinuation (see also Section 7.4.3.3).
- Any Grade 2 or higher non hematologic toxicity atezolizumab-related not resolving at Grade 1 or better within 12 weeks despite symptomatic therapy
- Pregnancy as confirmed by a positive serum beta-HCG test. Pregnancy will be reported under the same timelines as a serious adverse event.
- At specific request of the sponsor.

Patients may be withdrawn from the study treatment if any of the following occurs:

- If the patient develops conditions which would have prevented his/her entry into the study according to the inclusion / exclusion criteria, he/she must be withdrawn immediately if safety is concerned; in other cases, the investigator will decide whether there is a conflict for the patient to continue.

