	Initiate treatment with anti-thyroid drugs such as methimazole or carbimazole as needed
	Refer to endocrinologist
	Resume atezolizumab when symptoms are controlled and thyroid function is improving
	In case of Grade 4 immune-mediated hyperthyroidism, permanently discontinue atezolizumab and contact the sponsor $^{\rm c}$

23 MAY 2023 Version 6.0 Page: 71 of 181

Table 7–8: Management guidelines for endocrine events

Event	Management
Symptomatic adrenal	Withhold atezolizumab ^a
insufficiency Grade 2-4	Refer patient to endocrinologist
	Perform appropriate imaging
	Initiate treatment with 1–2 mg/kg/day intravenous methylprednisolone or equivalent and convert to 1–2 mg/kg/day oral prednisone or equivalent upon improvement
	Resume atezolizumab if event resolves to Grade 1 or better and patient is stable on replacement therapy (if required) within 12 weeks ^{a, b}
	Permanently discontinue atezolizumab and contact sponsor if event does not resolve to Grade 1 or better or patient is not stable on replacement therapy within 12 weeks $^{\rm a,b,c}$
Hyperglycemia, Grade 1 or 2	Continue atezolizumab
	Initiate treatment with insulin if needed
	Monitor for glucose control
Hyperglycemia, Grade 3 or 4	Withhold atezolizumab
	Initiate treatment with insulin
	Monitor for glucose control
	Resume atezolizumab when symptoms resolve and glucose levels are stable

i.v. = intravenous; mIU = Milli international unit; MRI = magnetic resonance imaging; TSH = thyroid-stimulating hormone.
 a: If corticosteroids have been initiated, they must be tapered over ≥ 1 month to ≤ 10 mg/day oral prednisone or equivalent before atezolizumab can be resumed.

Severe cutaneous adverse reactions

Severe cutaneous adverse reactions are an identified risk of atezolizumab. Severe cutaneous adverse reactions are a heterogeneous group of immunologically mediated drug eruptions frequently associated with drug use including immune checkpoint inhibitors as a class. Although rare, these events are potentially fatal, and mainly constituted by erythema multiforme, acute generalised exanthematous pustulosis, SJS, TEN, and drug rash with eosinophilia and systemic symptoms.

The management of severe cutaneous adverse reactions will be as follows:

 For suspected severe cutaneous adverse reactions, refer patients to a dermatologist for further diagnosis and management

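### The protocol gives conflicting scopes for mandatory permanent discontinuation after Grade 4 toxicity, and states no precedence between Sections 6.4.1.3, 7.4.3.2 and 7.4.3.3

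*Protocol*

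**What the plan says.** Four places in the protocol bear on what happens after a Grade 4 toxicity.

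- **Section 7.4.3.2, text above Table 7-3, and the table itself.** The text says "Patients who experience a Grade 4 toxicity must discontinue study drug permanently", and the Grade 4 row says "Discontinue study treatment permanently". The table's title sets aside hyperphosphatemia, liver toxicity and retinal disorders. Footnote a sets aside alopecia, fatigue and controlled nausea or vomiting, and adds: "Laboratory abnormalities of any grade will not be considered toxicity unless deemed clinically significant by the investigator". Hematological toxicity is not set aside.
- **Section 7.4.3.2, paragraph before Table 7-2.** "Patients who experience a Grade 4 non-hematological toxicity, and any other toxicity defined as withdrawal criteria will be permanently withdrawn from the study treatment".
- **Section 6.4.1.3, list of events for which the patient must be withdrawn from study treatment.** One item is "Grade 4 non-hematological toxicity (laboratory abnormalities of any grade will not be considered toxicity unless deemed clinically significant by the investigator".
- **Section 7.4.3.3, atezolizumab.** The list of reasons to withhold includes symptomatic adrenal insufficiency, Grade 3 or 4 hyperglycemia and Grade 3 or 4 infection, with resumption possible on recovery to Grade 0 or 1. Table 7-8 puts symptomatic adrenal insufficiency of Grades 2 to 4 in one row: "Resume atezolizumab if event resolves to Grade 1 or better and patient is stable on replacement therapy (if required) within 12 weeks". Permanent discontinuation follows only if that condition is not met.

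The definitions of terms and Section 7.2 make study drug mean either agent, and study treatment mean the two together.

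**The concern.** These are mandatory instructions, and they differ in two ways.

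The first is the kind of event. One part of Section 7.4.3.2 stops treatment after Grade 4 toxicity without a hematological exemption. Another part of the same section, and Section 6.4.1.3, attach the rule to non-hematological events only.

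The second is the drug. Section 6.4.1.3 takes the patient off both agents for a Grade 4 non-hematological toxicity, while Section 7.4.3.3 provides for atezolizumab to be resumed after some of those same events.

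At stake are the safety of patients still on treatment and the consistency of what is reported. Reasons for stopping study treatment are tabulated (Protocol 10.3.1, SAP 6.1.1). Treatment duration, dose received and dose modification are summarized (SAP 6.4). Events leading to interruption and events leading to discontinuation are listed separately (SAP 6.4.2). If sites follow different passages, those outputs partly reflect the passage chosen and not only the toxicity.

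**Working it through.** The plan states no figure on this point, so the check is a comparison of the texts. Each row takes a Grade 4 event that counts as a toxicity.

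| Grade 4 event | 7.4.3.2, sentence and Table 7-3 | 7.4.3.2, earlier paragraph | 6.4.1.3 | 7.4.3.3 and Table 7-8 (atezolizumab) |
|---|---|---|---|---|
| Hematological, clinically significant | Permanent stop | Not named | Not named | No item in either list |
| Symptomatic adrenal insufficiency | Permanent stop | Withdraw from both drugs | Withdraw from both drugs | Withhold, may resume |
| Infection | Permanent stop | Withdraw from both drugs | Withdraw from both drugs | Withhold, may resume |
| Hyperglycemia, clinically significant | Permanent stop | Withdraw from both drugs | Withdraw from both drugs | Withhold, may resume |

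1. **Hematological events.** The laboratory proviso in footnote a narrows the conflict to clinically significant events but does not remove it. For those events Table 7-3 requires a stop. The other two places carry a qualifier that leaves them out. Section 7.4.3.2 also provides for re-treatment at a reduced rogaratinib dose after a DLT and does not exclude hematological DLTs from this.

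2. **Non-hematological events.** The adrenal row of Table 7-8 concerns symptomatic disease, so the laboratory proviso in Section 6.4.1.3 offers no way out. It does not help for infection either. For hyperglycemia the conflict arises only if the finding is judged clinically significant.

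3. **Which drug.** The sentence above Table 7-3 speaks of study drug and the table below it of study treatment. By the protocol's own definitions these differ, so even within that passage it is unclear whether one agent or both must stop.

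4. **Precedence.** Section 6.4.1.3 refers to Section 7.4.3.3, but in a separate item on atezolizumab-related toxicity of Grade 3 or higher. That reference does not qualify the Grade 4 item. No sentence ranks the three sections.

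5. **Size per patient.** The documents give no expected count of Grade 4 events. One patient moved between withdrawn and continued changes the discontinuation percentage by 100/n points. For the planned sizes in Section 10.4, and assuming all these patients are treated, this is 100/26 = 3.8, 100/30 = 3.3 and 100/50 = 2.0 points.

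**The case against.** Three points can be made for the text as it stands.

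First, the narrower passages say which events require withdrawal. They do not say that only those events do. A site that follows the broader rule satisfies all of them on the hematological question, and Section 6.4.1.3 also lets the investigator stop for any other sufficiently serious reaction. This is right as logic: re-treatment after a hematological Grade 4 event is an inference and is nowhere stated. But the word non-hematological then has no function in two mandatory passages, and a site relying on Section 6.4.1.3 has no reason to think such a patient must stop.

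Second, Section 7.4.3.3 is about atezolizumab and Table 7-3 is about rogaratinib, so rules for two drugs are being compared. Section 6.4.1.3 has its own atezolizumab items, one of them with a 12-week limit like that in Table 7-8. Section 7.4.3.3 also allows resumption, with documented approval, after recovery from a life-threatening immune-mediated event. A reader could well conclude that Section 7.4.3.3 is meant to govern atezolizumab. That may be the intention, but it is not written, and the Grade 4 item in Section 6.4.1.3 covers both drugs without exception.

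Third, the study is late in its course: the Amendment no. 3 summary says that remaining patients had been treated for at least 2 years. This limits the number of patients affected from now on. Version 6.0 still revises Section 7.4.3.3, however, so these rules are in force for patients on treatment.

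**Conclusion.** The contradiction stands on the text. Its practical size cannot be given as a total, only per patient as above. It rests on two assumptions: that the event counts as a toxicity, and that laboratory findings are clinically significant.

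A reader might go further and infer that membership of the MTD analysis set, and so the mTPI recommendation, depends on the passage followed. Table 10-1 makes this tempting: 3 DLTs in 5 patients gives D and 3 in 6 gives S, so dropping one patient without a DLT would change the action. Recomputing the rule with the Beta(1,1) prior reproduces both cells. The documents do not support the step before that, for these reasons:

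- Section 7.4.3.1 counts as a DLT a rogaratinib-related toxicity thought to warrant withholding for more than 3 consecutive days, and also a clinically relevant toxicity that prevents the start of Cycle 2. A patient permanently stopped in Cycle 1 for a related, clinically significant Grade 4 event would ordinarily meet one of these. That patient enters the MTD set as a discontinuation due to a DLT (Protocol 10.2, SAP 5.1) and is not replaceable under Section 6.4.2.
- Related Grade 4 adrenal insufficiency in Cycle 1 is a DLT anyway, because it is a non-hematological toxicity of Grade 3 or higher and is not among the exceptions.
- An example built on a short neutropenia needs a CTCAE grade cut-point, which the documents do not give.
- Section 5.1 treats the mTPI output as guidance, to be weighed with clinical, PK and safety data.

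A case in which DLT status differs can still be imagined, such as a short hold followed by resumption under the narrower reading. It takes several assumptions, and nothing here rests on it. The effect shown is on withdrawals, exposure and discontinuation reasons.

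**What to change.** Reconcile Section 6.4.1.3, both statements in Section 7.4.3.2, Table 7-3, the withhold list in Section 7.4.3.3 and Table 7-8 into one statement that says:

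- which Grade 4 events require permanent discontinuation;
- for each, whether this applies to rogaratinib, atezolizumab or both, using the defined terms consistently;
- which of Sections 6.4.1.3, 7.4.3.2 and 7.4.3.3 takes precedence where they overlap.

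Which events belong on that list is a clinical decision for the sponsor and investigators, and none is proposed here.

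The cost is protocol wording in three sections and two tables. No new data, sample size work or SAP change is needed. There is a precedent: the Amendment no. 2 summary records that the Grade 3 row of the same Table 7-3 was aligned with the rest of the protocol to remove an inconsistency.
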